6.2.2 On-Study/On-Interventions Evaluations/procedures

At each study visit, subjects will undergo the following assessments:

- Hoehn & Yahr
- Concomitant medication review
- Orthostatics
- Height and weight
- Vital signs
- Physical examination
- Neurological examination
- MDS-UPDRS Motor Assessment
- Cognitive Assessments
- Behavioral Assessments
- Sleep Assessments
- Fall Assessments
- Speech Assessments
- Motor Assessments

- Blood Draw
- Drug accountability/compliance
- Adverse Event Review

The likelihood of adverse events is highest near the initiation of study drug or at the time of dose escalation³⁴. Therefore, subjects will be contacted via telephone the following 3 weeks (weeks 3, 4 & 5) after starting study drug and after the 2 week visit. They will then be seen halfway through the study at 6 weeks. They will again be contacted 9 weeks after their baseline visit via telephone by the research coordinator, and their final visit will be 12 weeks after their baseline visit.

6.2.3 Study Medication Discontinuation Evaluations/procedures

Study medication discontinuation will occur under the following circumstances:

- Completion of study
- Presence of orthostatic hypotension
- Blood pressure of ≤90/60
- Participant initiates prohibited medication
- Participant reports unwillingness to continue with study due to intolerable side effects

If any of the above occurs, participants will be asked to come in for an end-of-study visit as soon as possible. All assessments outlined in the SoA will be performed at the end-of-study visit. Participants will not be required to continue for future follow-up appointments after discontinuation of treatment. Participants who experience adverse effects will immediately discontinue study treatment and will not be considered for inclusion in further evaluations.

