4.3 Lifestyle Considerations

No specific restrictions on lifestyle and/or diet will be placed on the subject during the study. If a participant is prescribed an α-1 antagonist that is indicated for their care, they will be withdrawn early from the study to 1) avoid the risk for harmful side effects and 2) to maintain the integrity of blinding.

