4.4 Subject Withdrawal Criteria

Subjects are free to withdraw from the study at any point. Subjects will be withdrawn from the study if they experience serious and/or persistent side effects during the study that, in the opinion of the site PI, are thought to be related to the study drug. Examples include but are not limited to persistent and symptomatic orthostatic hypotension, persistent peripheral edema, persistent drowsiness that significantly affects activities of daily living, significant weakness, or falls. If any of these side effects occur, the site PI will be asked to make a recommendation regarding whether continuation of the study treatment will place the subject at any undue risk. If so, the subject will be immediately withdrawn from the study.

Withdrawn subjects will not be replaced. Should a subject withdraw from the study despite all efforts to maintain follow-up every effort should be made to obtain an in-person final visit, which should include all assessments that would be obtained in the final drug visits (see Section 6).

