5.3.2 Prohibited Medications/Interventions

Subjects are prohibited from taking doxazosin, alfuzosin, prazosin, terazosin, urapadil, or tamsulosin during this study. If one of these medications is prescribed during the course of the study, the participant will be informed that initiation of any of these treatments will result in their immediate withdrawal from the study. They may decide if they wish to receive the prescribed treatment from their outside provider. If the subject decides to not initiate the prohibited treatment, they may remain in the study.

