6.2.4 On Study/Off-Intervention Evaluations

This trial will follow an intention-to-treat design. Subjects who discontinue study medication (see section 6.2.3) will be asked to continue to be followed for the remainder of the study, but will not be taking a study intervention. The following assessments will be performed at all on study/off-intervention visits:

- Hoehn & Yahr
- Concomitant medication review
- Orthostatics
- Height and weight
- Vital signs
- Physical examination
- Neurological examination
- MDS-UPDRS Motor Assessment
- Cognitive Assessments
- Behavioral Assessments
- Sleep Assessments
- Fall Assessments
- Speech Assessments
- Motor Assessments
- Blood draw

If participants are unable or unwilling to continue with the regularly-scheduled assessments after discontinuation of the study intervention, they will be encouraged to return to the study site for a final evaluation that will include the same assessments as listed above.

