8 CRITERIA FOR INTERVENTION DISCONTINUATION

Study medication discontinuation will occur under the following circumstances:

- Completion of study
- Presence of orthostatic hypotension
- Blood pressure of $\leq 90/60$
- Participant initiates prohibited medication
- Participant reports unwillingness to continue with study due to intolerable side effects

Participants who discontinue study medication will be encouraged to undergo all remaining study assessments.

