9.3 Data Monitoring

All aspects of the study will be monitored by the PI of the study. Monitoring will be conducted according to Good Clinical Practice and applicable government regulations. The investigator agrees to allow monitors access to the clinical supplies, dispensing and storage areas, and to the clinical files of the study subjects, and, if requested, agrees to assist the monitors.

An adverse event (AE) is any unfavorable and unintended sign (including a clinically significant abnormal laboratory finding, for example), symptom, or disease temporally associated with a study, use of a drug product or device whether or not considered related to the drug product or device. FDA and Office of Human Research Protection (OHRP) requirements for reporting AEs will be followed. Subjects will be monitored for AEs from the time they sign consent until 30 days following permanent discontinuation of study drug. At that point, all ongoing AEs will be followed to resolution, but no new AEs will be recorded.

The PI and research team (co-Investigators, research nurse, clinical trial coordinator) are responsible for identifying and reporting AEs and determining the relationship of the event to the study drug/study procedures.

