9.4 Data Analyses

The following outcome measures will be analyzed under an intention-to-treat protocol. All randomized individuals will be included regardless of their final treatment status.

- Primary Outcome
 - Rate of drop out between groups
 - Chi-square
 - Rate of adverse events between groups
 - Chi-square
- Secondary outcomes
 - Prevalence of orthostatic hypotension between placebo and active group
 - Chi-square
 - Prevalence of falls between placebo and active group
 - Chi-square
 - Differences in overall compliance between placebo and active group
 - Linear mixed effect models that includes compliance at each study visit for each participant
- Exploratory outcomes
 - Difference in ATP levels in red blood cells and brain within subjects before and after taking study drug on day 1
 - Paired samples t-test
 - Difference in ATP levels in red blood cells and brain within subjects at 6 and 12 weeks compared to baseline reading

- Paired samples t-test
- Difference in ATP levels in red blood cells and brain between groups at 6 weeks and 12 weeks
 - Independent samples t-test
- Slope of change over 12 weeks of the MDS-UPDRS Part 1
 - LMER
- Slope of change over 12 weeks of the MDS-UPDRS Part 2
 - LMER
- Slope of change over 12 weeks of the MDS-UPDRS Part 3
 - LMER
- Slope of change over 12 weeks of the MDS-UPDRS Part 4
 - LMER
- Absolute change over 12 weeks of the MDS-UPDRS Parts 1, 2, 3, 4, and TMS
 - Independent samples t-tests
- Slope of change over 12 weeks of MDS-UPDRS TMS (direct comparison for efficacy)
 - LMER
- Slope of change over 12 weeks of the Hoehn & Yahr Score
 - LMER
- Slope of change over 12 weeks of all cognitive assessments between placebo and active group
 - LMER
- Slope of change over 12 weeks of sleep assessments between placebo and active group
 - LMER
- Slope of change over 12 weeks of behavioral assessments between placebo and active group
 - LMER

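### Section 6.2.3 bars participants with adverse effects from further evaluations, contradicting the off-drug follow-up in Sections 6.2.4 and 8

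*Combined protocol and SAP*

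**What the plan says.** Section 6.2.3 lists the reasons for stopping study drug: study completion, orthostatic hypotension, blood pressure at or below 90/60, starting a prohibited drug, and unwillingness to go on because of intolerable side effects. It asks for an end-of-study visit soon after a stop and says later appointments are not required. Its last sentence then goes further: "Participants who experience adverse effects will immediately discontinue study treatment and will not be considered for inclusion in further evaluations".

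Other current text points the other way:

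- Section 6.2.4: "Subjects who discontinue study medication (see section 6.2.3) will be asked to continue to be followed for the remainder of the study".
- Section 8: "Participants who discontinue study medication will be encouraged to undergo all remaining study assessments".
- Section 9.3: "Subjects will be monitored for AEs from the time they sign consent until 30 days following permanent discontinuation of study drug".
- Section 9.4, on the analysis population: "All randomized individuals will be included regardless of their final treatment status".

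Section 7 stops drug only for side effects that the participant or the investigator finds intolerable. Section 4.4 has a further rule: "Subjects will be withdrawn from the study if they experience serious and/or persistent side effects during the study", provided the site PI thinks them drug-related. It then asks for every effort to obtain a final in-person visit with the full set of final assessments.

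**The concern.** The trial's stated purpose is safety, tolerability and feasibility, and Section 2.3 says it will directly assess orthostatic hypotension and falls. The closing sentence of 6.2.3 removes from observation the participants who bear on that question, because they had an adverse effect. If terazosin causes more adverse effects than placebo, the loss would also be uneven between arms. With 10 participants per arm, each person lost is 1/10 = 10% of an arm.

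Site staff also have no way to comply with both 6.2.3 and 6.2.4. Who stays in follow-up would depend on which section a coordinator happens to apply.

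**Working it through.** There is no figure in the plan to reproduce: Section 9.2 sets the sample size by funding and gives no expected stop rate. The check is a comparison of texts, followed by a count of the contacts at stake.

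**1. Is the conflict real on follow-up?** Section 6.2.4 refers to 6.2.3 by number, so both sections address the same people. The statement in 6.2.3 that later appointments are not required is compatible with 6.2.4, which only asks. The final sentence is not: it takes the participant out of consideration for later evaluations, while 6.2.4 and 8 invite the participant to them.

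**2. Does a narrow reading remove it?** Suppose the sentence means only the intolerable side effects already in 6.2.3's list. The trigger problem then disappears, but the bar on further evaluations still contradicts 6.2.4 and 8 for exactly those people.

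**3. Is the literal trigger out of line?** Yes. The sentence states no threshold. The 6.2.3 list and Section 7 require intolerable effects, and 4.4 requires serious and/or persistent effects thought to be related. Section 10.3.1.3 grades events from mild upward and records the action taken with study drug, which presupposes that some participants with an event stay on treatment.

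**4. What would be lost?** Inputs from Sections 6.1 and 6.2.2, taking week *w* as day 7*w*:

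- Visits: days 14, 42 and 84 (weeks 2, 6, 12).
- Calls: days 21, 28, 35 and 63 (weeks 3, 4, 5, 9).
- Adverse event window from Section 9.3: stop day + 30.

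Contacts lost are those after stop day *s*. Contacts in the window are those after *s* and no later than *s* + 30. The end-of-study visit is assumed to fall on the stop day; a later one would replace some of these contacts.

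| Stop | Visits lost | Calls lost | Window ends | Lost contacts in window |
|---|---|---|---|---|
| Week 2 (day 14) | 2 (days 42, 84) | 4 (days 21, 28, 35, 63) | 14 + 30 = day 44 | 4 (days 21, 28, 35, 42) |
| Week 4 (day 28) | 2 (days 42, 84) | 2 (days 35, 63) | 28 + 30 = day 58 | 2 (days 35, 42) |
| Week 6 (day 42) | 1 (day 84) | 1 (day 63) | 42 + 30 = day 72 | 1 (day 63) |

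Early stops are the relevant case: Section 6.2.2 says adverse events are most likely around initiation and dose escalation, and Section 5.1 titrates over the first four weeks.

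**5. What do those contacts carry?** In the Section 6.1 schedule, falls and adverse event review occur at every contact from week 2, while vital signs and orthostatics occur at the visits. A week-2 or week-4 stop therefore costs both the week-6 and week-12 blood pressure readings needed for the secondary outcome; a week-6 stop costs the week-12 reading. All of these would be off-drug values. After the 30-day window Section 9.3 records no new adverse events, so the later contacts lose falls and blood pressure but no planned new-event data.

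**The case against.** The strongest reply is that the sentence is loose drafting at the end of a section whose own list supplies the threshold. It speaks of adverse effects, a term Section 2.3 uses for effects of terazosin, whereas the defined term covering unrelated occurrences is adverse event. That is a fair point. A reader might infer that any mild or unrelated event ends participation. The words allow it, but the surrounding text makes it an unlikely intention. The contradiction on follow-up survives either reading (step 2).

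Other stronger readings are also not supported:

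- **That 9.4 and 9.3 are flatly contradicted.** Section 9.4 says who is analysed. Everyone randomized can still be counted with later values missing, so the sentence sits poorly with intention-to-treat without contradicting it. Adverse event monitoring under 9.3 could be run separately, although that section names no contacts of its own.
- **That 4.3 and 5.3.2 are the same error.** Section 4.3 says of a participant prescribed an alpha-1 antagonist "that is indicated for their care, they will be withdrawn early from the study", and 5.3.2 that "initiation of any of these treatments will result in their immediate withdrawal from the study". Section 4.3 gives reasons: harm and blinding. There is a mismatch, since 6.2.3 and 8 treat starting such a drug as a study-drug stop that 6.2.4 would follow up. But later readings would be confounded, so continued follow-up there is a trade-off.
- **That 4.4 ends all observation.** It still seeks a full final visit.
- **That adverse event review is missing off drug.** The 6.2.4 list omits it, but Section 10.3.1.3 requires the question at every visit and call, and the 6.1 schedule has it at every contact from week 2.
- **That the undefined drop-out rate changes the primary result.** Section 3.3 defines only completion, and 9.1.2 lists study discontinuation separately without defining it. Any effect on the test would rest on invented counts, so this is missing detail.

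**Conclusion.** The last sentence of 6.2.3 is wrong as written and should be fixed. Confidence is high for the conflict with 6.2.4 and 8, which rests on current text alone.

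The size is moderate. Per affected participant, up to 6 scheduled contacts are lost after a week-2 stop (4 in the 30-day window), up to 4 after week 4 (2 in the window) and up to 2 after week 6 (1 in the window). These are upper bounds that assume the end-of-study visit takes place at the stop. How many participants would be affected cannot be derived, because the plan gives no expected rate of stopping.

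Two things limit the harm. The end-of-study visit captures data near the stop. And the primary outcome counts participants with drug-related events, so someone removed because of such an event has already been counted. A reader might infer that the blood pressure comparison would be biased in a particular direction; the documents do not allow its size or sign to be worked out.

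**What to change.** - Delete the last sentence of 6.2.3. Keep the stopping reasons in 6.2.3 and 8, and the intolerable threshold in 7.
- State that 6.2.4 and 8 govern everyone who stops study drug: asked, but not required, to attend the remaining visits and calls, with adverse event review through at least 30 days after the stop.
- Amend 4.4 so that a side-effect stop ends study drug and not follow-up.
- Minor clarification: report permanent study-drug discontinuation and study withdrawal as separate counts, and say before unblinding which of them is the primary drop-out rate.

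The cost is a wording amendment, with the IRB approval that Section 6.3.7 requires, and a few off-drug visits that 6.2.4 already provides for. Those visits will not recover the on-drug blood pressure effect, and participants remain free to decline them.

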7 MANAGEMENT OF ADVERSE EXPERIENCES

The expected adverse experiences from use of TZ include orthostatic hypotension, palpitations, peripheral edema, nausea, asthenia, dizziness, headache, somnolence, nasal congestion, syncope, intraoperative floppy iris syndrome, and priapism. Participants who experience side effects that are found to be intolerable by the subject or the site investigator will discontinue study drug. If discontinuation of the study drug occurs in between visits, subjects will be encouraged to return to the site for their end of study assessment.

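### The last sentence of 6.2.3 bars participants with adverse effects from further evaluations, against the continued follow-up in 6.2.4 and section 8 and the 30-day adverse event monitoring in 9.3

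*Combined protocol and SAP*

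**What the plan says.** Section 6.2.3 lists the reasons for stopping study drug: study completion, orthostatic hypotension, low blood pressure, a prohibited medication, and "Participant reports unwillingness to continue with study due to intolerable side effects". It asks for a prompt end-of-study visit with all scheduled assessments, then adds: "Participants will not be required to continue for future follow-up appointments after discontinuation of treatment". It closes with: "Participants who experience adverse effects will immediately discontinue study treatment and will not be considered for inclusion in further evaluations".

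Other sections say the following.

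- **6.2.4** declares an intention-to-treat design, refers back to 6.2.3, and says that subjects who discontinue study medication "will be asked to continue to be followed for the remainder of the study". A final evaluation is the fallback for those unable or unwilling to continue.
- **Section 7**: "Participants who experience side effects that are found to be intolerable by the subject or the site investigator will discontinue study drug".
- **Section 8** repeats the 6.2.3 stop list and adds: "Participants who discontinue study medication will be encouraged to undergo all remaining study assessments".
- **9.3**: "Subjects will be monitored for AEs from the time they sign consent until 30 days following permanent discontinuation of study drug". Ongoing events are then followed until they resolve, and new ones are no longer recorded.
- **4.4** withdraws subjects from the study for serious and/or persistent side effects that the site PI thinks are drug-related. The PI is asked whether continuing is an undue risk, and a final visit is sought.

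**The concern.** The closing sentence of 6.2.3 does two things. It gives a stop trigger with no limit on severity, tolerability or relatedness, and it shuts the affected participants out of later evaluations. The second is the more serious. Elsewhere the protocol wants people who stop drug to be seen to the end. This sentence singles out those who stopped because of an adverse effect and says the opposite.

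The primary outcome is safety and tolerability, judged by drug-related adverse events and drop-out. Blood pressure change at weeks 6 and 12 is a secondary outcome. Missing data that arise because a participant had an adverse effect are not a random subset. Two staff members, one following 6.2.3 and one following 6.2.4, would also handle the same participant differently.

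**Working it through.** The plan states no power, drop-out or event-rate figure to reproduce (9.2 bases the sample size on funding and resources). The check is a comparison of texts, then a count of scheduled contacts.

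**Step 1: what triggers the stop?**

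- 6.2.3, last sentence: adverse effects, unqualified.
- 6.2.3 bullet, repeated in section 8: intolerable side effects, with the participant unwilling to go on.
- Section 7: intolerable to the subject or the site investigator.
- 4.4 (study withdrawal): serious and/or persistent, and judged drug-related.

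The last sentence is the loosest of the four.

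**Step 2: what happens afterwards?**

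- 6.2.3, last sentence: no inclusion in further evaluations.
- 6.2.4: asked to stay in follow-up to the end.
- Section 8: encouraged to complete all remaining assessments.
- 9.3: adverse events monitored for 30 more days.

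**Step 3: does a narrow reading remove the conflict?** Suppose the sentence means only the listed stop reasons. Step 1 is then largely settled. Step 2 is not, because those are exactly the people whom 6.2.4 (by its reference to 6.2.3) and section 8 want followed.

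**Step 4: which scheduled data are at stake?** Inputs from the Schedule of Activities (6.1): adverse event reviews at weeks 2, 3, 4, 5, 6, 9 and 12, which is 7 contacts; blood pressure outcome visits at weeks 6 and 12 (9.1.2). Week n is taken as day 7n, so the reviews fall on days 14, 21, 28, 35, 42, 63 and 84.

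Stop at the week 2 visit:

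- Window under 9.3: 14 + 30 = day 44.
- Reviews left: 7 − 1 = 6. Inside the window: days 21, 28, 35, 42 (4). Outside: days 63, 84 (2).
- Blood pressure outcome visits lost: weeks 6 and 12, both.

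Stop at the week 6 visit:

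- Window under 9.3: 42 + 30 = day 72.
- Reviews left: 2. Inside: day 63 (1). Outside: day 84 (1).
- Blood pressure outcome visits lost: week 12.

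If 9.3 is followed alongside the bar, the reviews lost are those outside the window: 2 after a week 2 stop, 1 after a week 6 stop. If the bar is taken to override 9.3, all remaining reviews go: 6 and 2. The falls question, a secondary outcome, is scheduled at the same contacts.

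**Step 5: scale.** With 10 per arm, one participant is 1/10 = 10% of an arm. The documents give no rate of adverse effects, so the number of participants affected cannot be derived, and none is assumed here.

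**The case against.** **The sentence may be shorthand.** It closes a paragraph about the listed stop reasons. Elsewhere, the action taken is recorded for each event (10.3.1.3), events that lead to permanent discontinuation are singled out (10.3), and the PI advises on continuation (4.4). Those provisions make little sense if every event stops drug. This stands. A reader might infer that any mild, tolerable effect ends treatment and so inflates drop-out. That is the less likely reading, and drop-out has no separate definition that would make every drug stop count.

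**9.3 protects adverse event data.** A reader might infer that a week 2 stop loses 6 of the 7 reviews. That follows only if the bar overrides 9.3, which no text says. Under 9.3 no new event is recorded after the 30 days and ongoing ones are followed anyway, so the weeks 9 and 12 reviews would mainly track ongoing events. The blood pressure visits are the firmer loss.

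**Some apparent conflicts are not conflicts.** Follow-up that is not required can still be requested, so the sentence before the bar is compatible with 6.2.4. Section 9.4 says "All randomized individuals will be included regardless of their final treatment status", which sets who is analysed, not who attends. Still, keeping someone in the analysis set does not supply values that were never collected.

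**The end-of-study visit recovers data.** It gives one early measurement, not the scheduled week 6 or week 12 values.

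**Editing 6.2.3 alone is not enough.** Section 4.4 still withdraws participants from the study for side effects. This stands, and the fix covers it.

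**Conclusion.** The contradiction is real and rests on the text alone. The bar on further evaluations cannot be reconciled with 6.2.4 and section 8, and it sits against 9.3, on either reading of its trigger. The looser trigger is a second, lesser fault.

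Followed as written, the sentence removes later scheduled data from participants with adverse effects. A stop at week 2 costs both blood pressure outcome visits and the reviews at weeks 9 and 12, and also those at weeks 3 to 6 if the bar is taken to override 9.3. These counts assume a stop at the week 2 visit, week n as day 7n, and no contact after the end-of-study visit other than what 9.3 requires.

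A reader might go on to infer a bias for or against terazosin. The documents do not support that: there are no event rates, either arm could lose more participants, and the direction and size of any effect on the arm difference are unknown. The point should be fixed because it governs how the primary safety and tolerability data are collected and the correction is cheap.

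**What to change.** 1. In 6.2.3, replace the last sentence with the section 7 threshold: study drug stops immediately when either the subject or the site investigator finds a side effect intolerable. Delete the bar on further evaluations.
2. State in 6.2.3 that anyone who stops drug early is asked to keep to all scheduled visits and calls under 6.2.4 and section 8. Keep the prompt visit as a safety visit. A single final evaluation applies only to those unable or unwilling to continue.
3. Add adverse event review to the 6.2.4 list. It appears in 6.2.2 and 6.2.5 but not there, so the off-drug visits do not now provide for the monitoring in 9.3.
4. Align 4.4 so that side effects lead to stopping study drug with follow-up under 6.2.4. Withdrawal from the study would then follow only if the subject chooses it.

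The cost is a protocol revision with IRB approval. Under 6.3.7, updated written consent is also needed if the revision is judged to change the number or frequency of evaluations. It needs no extra patients, and no visits beyond those already scheduled apart from the prompt visit that 6.2.3 already requests.
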